7.2.5 Exceptions to the Definition of SAE

Certain hospitalizations or prolongation of hospitalizations should not be considered SAEs, including those that meeting the following criteria:

- 7.2.5.1 An admission resulting in a hospital stay of less than 12 hours.
- 7.2.5.2 An admission that is pre-planned (i.e. elective or scheduled surgery arranged prior to the start of the study).
- 7.2.5.3 An admission that is not associated with an AE (i.e. social hospitalization for purposes of respite care).

7.2.6 Unanticipated Problems Involving Risks to Subjects or Others (UPIRSO)

A UPIRSO includes events that meet ALL of the following criteria:

- 7.3.3.1.1 Are unanticipated in terms of nature, severity, or frequency;
- 7.3.3.1.2 Place the research subject or others at a different or greater risk of harm; AND
- 7.3.3.1.3 Are deemed to be related or possibly related to participation in the study.

7.3 ADVERSE EVENT REPORTING

7.3.1 Routine Reporting

All routine adverse events, such as those that are expected, or are unlikely or definitely not related to study participation, are to be reported on the appropriate eCRF according to the time intervals noted in the Schedule of Events. Routine AEs will be reviewed by the Data Monitoring Committee (DMC) according to the study's phase and risk level, as outlined in the DSMP.

7.3.2 Steps to determine if expedited reporting is required

This includes all events that occur within 30 days of the last dose of protocol treatment. Any event that occurs more than 30 days after the last dose of treatment and is attributed (possibly, probably, or definitely) to the agent(s) must also be reported accordingly.

- 7.3.2.1 Identify the type of adverse event using the NCI CTCAE v 4.0.
- 7.3.2.2 Grade the adverse event using the NCI CTCAE v 4.0.
- 7.3.2.3 Determine whether the adverse event is related to the protocol therapy.

Attribution categories are as follows:

- 7.3.2.3.1 Definite: AE is clearly related to the study treatment.
- 7.3.2.3.2 Probable: AE is likely related to the study treatment.
- 7.3.2.3.3 Possible: AE may be related to the study treatment.

7.3.2.3.4 Unrelated: AE is clearly NOT related to the study treatment.

7.3.2.4 Determine the prior experience of the adverse event.

Expected events are those that have been previously identified as resulting from administration of the agent. An adverse event is considered unexpected, for expedited reporting purposes only, when either the type of event or the severity of the event is not listed in:

7.3.2.4.1 the current protocol;

7.3.2.4.2 the drug package insert;

7.3.2.4.3 the current Investigator's Brochure.

7.3.3 Documentation of AEs

Each event should be described in detail along with start and stop dates, severity, relationship to regorafenib, action taken and outcome.

Any action on study treatment to resolve the AE is to be documented on the appropriate eCRF using the categories listed below:

- Drug withdrawn
- Drug interrupted
- Dose reduced
- Dose not changed
- Dose increased
- Not applicable
- Unknown

In addition, the outcome of the AE is to be documented as follows:

- Recovered/resolved
- Recovering/resolving
- Recovered/resolved with sequelae
- Not recovered/not resolved
- Fatal
- Unknown

7.3.4 Expedited Reporting of SAEs

Completion of the Medwatch form is the preferred method of reporting. This form can be found at: <http://www.fda.gov/medwatch/>.

7.3.4.1 Reporting to the Northwestern University QAM/DMC

All SAEs must be reported to the assigned QAM within 24 hours of becoming aware of the event. Completion of the NU CRO SAE Form, provided as a separate document, is required.

The completed form should assess whether or not the event qualifies as a UPIRSO. The report should also include:

- Protocol description and number(s)
- The patient's identification number
- A description of the event, severity, treatment, and outcome (if known)
- Supportive laboratory results and diagnostics
- The hospital discharge summary (if available/applicable)

All SAEs will be reported to, and reviewed by, the DMC at their next meeting.

7.3.4.2 Reporting to the IRB

The following information pertains to the responsibilities of the lead site (Northwestern University). Additional participating sites should follow their local IRB guidelines for reporting to their local IRBs.

- Any death of an NU subject that is unanticipated in nature and at least possibly related to study participation will be promptly reported to the NU IRB within 24 hours of notification.
- Any death of an NU subject that is actively on study treatment (regardless of whether or not the event is possibly related to study treatment)
- Any death of a non-NU subject that is unanticipated and at least possibly related and any other UPIRSOs will be reported to the NU IRB within 5 working days of notification.
- All other deaths of NU subjects not previously reported, other non-NU subject deaths that were unanticipated and unrelated, and any other SAEs that were not previously reported as UPIRSOs will be reported to the NU IRB at the time of annual continuing review.

7.3.4.3 Reporting to the FDA

This applies to studies conducted under an IND or IDE, as set forth in the Code of Federal Regulations, Section 312.32

The FDA will be notified within 7 calendar days of any SAE that is associated with study treatment, is unexpected, and is fatal or life-threatening.

The FDA will be notified within 15 calendar days of any SAE that is associated with the study treatment, unexpected, and serious but not fatal or life-threatening. This includes any previous SAEs that were not initially deemed reportable, but are later determined to meet the criteria for reporting (i.e. by the DMC).

All other SAEs will be reported on an annual basis as part of the annual FDA report.

7.3.5 Pregnancies

The investigator must report to Bayer any pregnancy occurring in a study subject, or in his partner, during the subject's participation in this study. The report should be submitted within the same timelines as an SAE, although a pregnancy per se is not considered an SAE. For a study subject, the outcome of the pregnancy should be followed up carefully, and any abnormal outcome of the mother or the child should be reported. For the pregnancy of a study subject's partner, all efforts should be made to obtain similar information on course and outcome, subject to the partner's consent. For all reports, the forms provided are to be used.

8.0 DRUG INFORMATION

8.1 SUPPLY AND STORAGE GUIDELINES

Regorafenib tablets will be packaged in high density polyethylene bottles with a white child resistant closure and induction seal. Each bottle includes 30 tablets and a 3-gram desiccant. The bottles will have a label affixed containing study identification, product identification, and quantity of tablets. Once the drug has been received it must be kept in a secure, dry location. Study drug must be stored in its original bottle at a temperature not above 25°C (77°F).

The study drug must be exclusively used for the investigation specified in this protocol and it will only be accessible to authorized staff.

8.2 DOSAGE AND ADMINISTRATION

The starting dose for all subjects on this study will be 160 mg daily (4 40 mg tablets). Regorafenib is administered orally. Please refer to Section 4 for further details regarding administration and dose modifications.

8.3 DRUG LOGISTICS AND ACCOUNTABILITY

All study drugs will be stored at the investigational site in accordance with Good Clinical Practice (GCP) and Good Manufacturing Practices (GMP) requirements and the instructions given by the clinical supplies department of the Institution and will be inaccessible to unauthorized personnel. Study drug for all sites will be shipped to the lead site (Northwestern University); the lead site will then be responsible for shipping drug to each of the participating sites. For questions about drug ordering or to request drug, please contact the following individual at Bayer Healthcare:

[name]
Bayer Healthcare - U.S. Medical Affairs
Investigator Sponsored Studies & Medical Education
[name]
Wayne, NJ 07470
Office: [contact]
Email: [contact]

8.3.1 Accountability

An adequate record of receipt, distribution, and return of all study drugs must be kept at each site. Patients will maintain a pill diary (see Appendices).

8.3.2 Destruction and Return

At the end of the study, unused supplies of regorafenib should be destroyed according to local institutional policies. A certificate of destruction should be sent to Bayer that outlines how much drug was destroyed. This may be sent via:

E-mail: [contact]

OR

[contact]

OR

Mail: [VP of Medical Affairs named in contract]

Bayer HealthCare Pharmaceuticals

[name]

Wayne, NJ 07470

9.0 STATISTICAL METHODS AND DETERMINATION OF SAMPLE SIZE

9.1 PRIMARY OUTCOME OF INTEREST

The primary endpoint will be progression-free survival at 4 months. Standard of care therapy currently provides a median PFS of about 3 months with a SD of approximately 2.5 months.

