1.1 BACKGROUND

Treatment of locally advanced and metastatic angiosarcoma is inadequate. Three phase II trials have been conducted in this setting. The first, ANGIOTAX, examined weekly paclitaxel in 30 patients with metastatic or unresectable angiosarcoma between April 2005 and October 2006 (1). Progression-free survival at 4 months was 45%. Response rate was less than 20% and median overall survival was 8 months. Despite these sobering results, retrospective analysis has demonstrated that weekly paclitaxel is slightly more active than single agent doxorubicin – the mainstay of metastatic soft tissue sarcoma therapy (2). A small retrospective series of 25 locally advanced or metastatic angiosarcoma patients treated between January 2008 and November 2010 suggests single agent gemcitabine may also have modest activity in this disease (3).

The inability of traditional cytotoxins to durably control angiosarcoma coupled with the observation this malignancy displays endothelial differentiation prompted interest in targeted anti-vascular therapies. Consequently, the two additional phase II trials in this setting have examined agents that antagonize the VEGF-VEGFR signaling axis. Agulnik and colleagues reported their phase II experience with bevacizumab in unresectable and metastatic angiosarcoma (4). Between August 2005 and April 2011, 23 angiosarcoma patients were treated with single agent bevacizumab. The median progression-free and overall survival were 3 months and 1 year, respectively. Responses were rare with only 2 (9%) experiencing a partial response. The French Sarcoma Group reported the third phase II trial in angiosarcoma examining the multi-targeted tyrosine kinase inhibitor, sorafenib, in 41 patients treated between June 2008 and June 2009 (5). Although progression-free and overall survival rates were disappointing, a 40% tumor control rate and 23% response rate were observed in patients previously treated with cytotoxic chemotherapy.

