9.3 TRIAL DESIGN AND DETERMINATION OF SAMPLE SIZE

A two-stage optimal Simon design will be employed to test the null hypothesis that the probability of progression-free survival of 4 months or greater (P) is ≤ 0.22 versus the alternative that the probability ≥ 0.45 . To test this hypothesis with adequate power, a first stage involving 12 patients will be completed. If > 3 patients achieve progression-free survival of 4 months, the trial will be continued for a total of 31 patients. If > 11 out of 31 patients achieve progression-free survival of 4 months, the trial will reject the hypothesis that $P \leq 0.22$ and conclude that $P > 0.45$,

To determine sample size, the following parameters were employed: $P0 = 0.22$, $P1 = 0.45$, $\alpha = 0.05$ and $\beta = 0.20$. Computations originally performed using software PASS (www.ncss.com).

N1	R1	PET	N	R	Avg N	α	β	Satisfied
26	9	0.000	26	9	26.00	0.043	0.194	Single Stage
7	0	0.176	26	9	22.66	0.042	0.199	Minimax
12	3	0.739	31	10	16.96	0.047	0.188	Optimum

Definitions:

N1 – sample size in the first stage

R1 – drug rejection number in the first stage

PET – probability of early termination of study

N – combined sample size of both stages

R – combined drug rejection number after both stages

Avg N – average sample size if this design is repeated many times

α – probability of rejecting that $P < P0$ when this is true

β – probability of rejecting that $P > P1$ when this is true

P0 – response proportion P of a poor drug

P1 – response proportion P of a good drug

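### The null rate P0 = 0.22 is unsourced and lies below the 4-month PFS rate implied by the protocol's own standard-of-care figure, so a positive result shows only P > 0.22

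*Combined protocol and SAP*

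**What the plan says.** Section 9.1 states that "The primary endpoint will be progression-free survival at 4 months" and follows this directly with the benchmark: "Standard of care therapy currently provides a median PFS of about 3 months with a SD of approximately 2.5 months". It names no population, line of therapy or source for that figure.

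In Section 9.3 the null is "the probability of progression-free survival of 4 months or greater (P) is ≤ 0.22", and the rate to be detected is set at 0.45 or more. The design is a Simon optimal two-stage design in which "a first stage involving 12 patients will be completed", and the trial continues to 31 patients if more than 3 succeed. The definitions under the design table describe P0 as the rate for a poor drug. No derivation of 0.22 appears in Section 9 or in the background.

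The final cut-off appears in two forms. The text of Section 9.3 requires more than 11 of 31. The optimum row of the table has R = 10, which means more than 10 of 31, with alpha 0.047 and beta 0.188. On success, the text says the trial will reject P ≤ 0.22 and conclude that P is above 0.45.

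For weekly paclitaxel, Section 1.1 reports "Progression-free survival at 4 months was 45" percent, which is numerically equal to P1.

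**The concern.** The only context given for the primary endpoint is a standard-of-care median of 3 months. By definition half of such patients are progression-free at 3 months, and a null of 0.22 at 4 months would require a very steep fall in one further month. If the standard-of-care rate at 4 months is well above 0.22, the stated alpha protects against a benchmark lower than the one the protocol quotes.

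What is at stake is the meaning of a positive result. Passing could be read as improvement over current treatment when it may reflect only performance similar to it. The planned conclusion that P is above 0.45 makes that over-reading more likely.

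**Working it through.** **Inputs.** Median 3 months and SD 2.5 months (Section 9.1). P0 = 0.22, P1 = 0.45, stage 1 of 12 patients with r1 = 3, N = 31, final R = 10 (table) or 11 (text), all from Section 9.3. The shape of the standard-of-care PFS distribution is an assumption, because the documents give none; Section 9.4 names the exponential only as an analysis model.

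**1. Reproduce the plan's design.** With success defined as more than R of 31,

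Pr(positive | p) = Σ (x = 4 to 12) Bin(x; 12, p) × Pr[Bin(19, p) ≥ R + 1 − x].

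- R = 10: 0.0468 at p = 0.22 and 0.8117 at p = 0.45 (beta 0.188). Early-termination probability is 0.739 and average N is 16.96. This matches the table's optimum row.
- R = 11: 0.0221 at p = 0.22 and 0.7519 at p = 0.45. The stated alpha and beta therefore belong to the table rule, not the text rule.

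**2. What 0.22 means on the time scale.** Under an exponential, median = 4 ln 2 / (−ln S(4)). S(4) = 0.22 gives 1.83 months. With the median held at 3 months, 0.22 would need an SD of about 1.21 (Weibull) or 1.24 (log-normal), about half the 2.5 stated.

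**3. The 4-month rate implied by Section 9.1.** Each two-parameter model below is solved for median 3 and SD 2.5.

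- Log-logistic, shape 3.242: S(4) = 1 / (1 + (4/3)^3.242) = 0.282
- Log-normal, σ = 0.622: S(4) = 1 − Φ(ln(4/3) / 0.622) = 0.322
- Gamma, shape 2.033, scale 1.753: S(4) = 0.344
- Weibull, shape 1.430, scale 3.877: S(4) = exp(−(4/3.877)^1.430) = 0.351
- Exponential, median 3 only: S(4) = 0.5^(4/3) = 0.397. Its SD is 3 / ln 2 = 4.33, so it does not match the stated 2.5.

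All five exceed 0.22.

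**4. Probability that a drug equal to standard of care is declared positive** (formula in step 1).

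| Model | S(4) | >10 of 31 (table) | >11 of 31 (text) | Stops at stage 1 |
|---|---|---|---|---|
| Null in Section 9.3 | 0.22 | 0.047 | 0.022 | 0.739 |
| Log-logistic | 0.282 | 0.190 | 0.118 | 0.547 |
| Log-normal | 0.322 | 0.337 | 0.239 | 0.427 |
| Gamma | 0.344 | 0.431 | 0.325 | 0.363 |
| Weibull | 0.351 | 0.462 | 0.355 | 0.343 |
| Exponential | 0.397 | 0.646 | 0.551 | 0.232 |

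At a rate rounded to 0.35, the two rules give 0.456 and 0.350.

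**5. The conclusion that P is above 0.45.** The smallest passing result under the text rule is 12/31 = 0.387, with an exact two-sided 95% lower limit of 0.218. Under the table rule it is 11/31 = 0.355. Both point estimates lie below 0.45. At a true P of 0.40, which is below 0.45, the trial would still be positive with probability 0.657 (table) or 0.564 (text).

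**6. Could Section 9.1 have meant the mean?** With mean 3 and SD 2.5:

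- Log-normal: σ² = ln(1 + (2.5/3)²) = 0.527, so σ = 0.726, and μ = ln 3 − 0.527/2 = 0.835. S(4) = 1 − Φ((ln 4 − 0.835) / 0.726) = 0.224.
- Gamma: shape (3/2.5)² = 1.44, and S(4) = 0.262.

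On that reading 0.22 would be close to the benchmark.

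**The case against.** The strongest reply is that P0 is defined as the rate of a poor drug. A null set at an uninteresting level of activity is a legitimate phase II choice. The trial enrols patients with progressive disease and up to four prior therapies (Section 3.1.7), whereas Section 9.1 does not say which patients its figure describes. The primary objective in Section 2.1 is to define the 4-month rate, and Section 9.4 already provides for exact confidence intervals. All of this stands, and it rules out several stronger readings:

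- A reader might infer that 0.22 contradicts Section 9.1. The documents never equate P0 with standard of care. The defect is an unsourced null that sits below the protocol's own benchmark.
- A reader might infer a single false-positive rate of 33% to 65%. That range uses only the permissive table cut-off and takes its top from an exponential whose SD disagrees with Section 9.1.
- A reader might infer from the paclitaxel figure that P1 merely equals standard care. Section 1.1 describes those patients as having metastatic or unresectable disease and states no prior-treatment requirement, so comparability is not established.
- A reader might infer that the end of Section 1.2 makes passing the route to phase III. It advises that later trials include an interim analysis, which is a caution.

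The reply does not explain where 0.22 comes from. It also does not defend the conclusion that P is above 0.45. If the aim is to screen for activity above a poor drug, Section 9.3 should say so.

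**Conclusion.** The point holds as an unjustified null and an overstated conclusion. If the Section 9.1 median and SD are taken at face value, the 4-month rate is about 0.28 to 0.35. A drug no better than that would pass with probability about 0.19 to 0.46 (table rule, alpha 0.047 at the null) or 0.12 to 0.35 (text rule, alpha 0.022 at the null). The exponential values of 0.65 and 0.55 are an upper illustration that honours the median but not the SD.

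These figures depend on the assumed distribution and on the Section 9.1 figure applying to the trial's population, which the documents do not establish. They also depend on the word median being intended, because under the mean reading the gap largely closes. The direction does not depend on the model: every model tried with median 3 months exceeds 0.22.

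Whatever the right benchmark, rejecting the null supports P > 0.22 and no more. It is not evidence of superiority to standard care or of P above 0.45.

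**What to change.** With N unchanged:

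1. In Sections 9.1 and 9.3, state the source and population for 0.22 and reconcile it with the standard-of-care figure, correcting whichever is wrong. Say explicitly whether the 3 months is a median or a mean.
2. In Section 9.3, replace the conclusion that P is above 0.45 with a statement that rejection shows P > 0.22, meaning activity above that of a poor drug, and does not show superiority to standard of care.
3. Reconcile the final cut-off between text and table, and add to the design table the probability of a positive result at higher true rates under the cut-off adopted:

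| True P | >10 of 31 | >11 of 31 |
|---|---|---|
| 0.28 | 0.18 | 0.11 |
| 0.32 | 0.33 | 0.23 |
| 0.35 | 0.46 | 0.35 |
| 0.40 | 0.66 | 0.56 |

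The cost is wording and a few added entries in the table. The price is that a positive trial supports a more modest claim. No fixed benchmark of 0.32 to 0.40 should be written into the plan, because that range depends on the model rather than on data in the documents.

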9.2 SECONDARY OUTCOMES OF INTEREST

Secondary endpoints of interest will include progression free rates at 3 and 6 months, median PFS, overall survival, response rates, duration of responses, rates of stable disease, safety and tolerability. Standard of care therapy currently provides a median overall survival of about 9 months with a SD of approximately 4 months.

9.3 TRIAL DESIGN AND DETERMINATION OF SAMPLE SIZE

A two-stage optimal Simon design will be employed to test the null hypothesis that the probability of progression-free survival of 4 months or greater (P) is ≤ 0.22 versus the alternative that the probability ≥ 0.45 . To test this hypothesis with adequate power, a first stage involving 12 patients will be completed. If > 3 patients achieve progression-free survival of 4 months, the trial will be continued for a total of 31 patients. If > 11 out of 31 patients achieve progression-free survival of 4 months, the trial will reject the hypothesis that $P \leq 0.22$ and conclude that $P > 0.45$,

To determine sample size, the following parameters were employed: $P0 = 0.22$, $P1 = 0.45$, $\alpha = 0.05$ and $\beta = 0.20$. Computations originally performed using software PASS (www.ncss.com).

N1	R1	PET	N	R	Avg N	α	β	Satisfied
26	9	0.000	26	9	26.00	0.043	0.194	Single Stage
7	0	0.176	26	9	22.66	0.042	0.199	Minimax
12	3	0.739	31	10	16.96	0.047	0.188	Optimum

Definitions:

N1 – sample size in the first stage

R1 – drug rejection number in the first stage

PET – probability of early termination of study

N – combined sample size of both stages

R – combined drug rejection number after both stages

Avg N – average sample size if this design is repeated many times

α – probability of rejecting that $P < P0$ when this is true

β – probability of rejecting that $P > P1$ when this is true

P0 – response proportion P of a poor drug

P1 – response proportion P of a good drug

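### The final success rule in section 9.3 (> 11 of 31) does not match the tabulated design (R = 10, so > 10 of 31), and as written it has 75% power, short of the planned 80%

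*Combined protocol and SAP*

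**What the plan says.** Section 9.3 of the combined protocol and SAP specifies a Simon two-stage optimal design with P0 = 0.22, P1 = 0.45, alpha = 0.05 and beta = 0.20.

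- **Stage 1 rule in the text:** "If > 3 patients achieve progression-free survival of 4 months, the trial will be continued for a total of 31 patients". Stage 1 has 12 patients.
- **Final rule in the text:** "If > 11 out of 31 patients achieve progression-free survival of 4 months", the trial rejects the hypothesis that P is at most 0.22.
- **Design table, Optimum row:** N1 = 12, R1 = 3, PET = 0.739, N = 31, R = 10, average N = 16.96, alpha = 0.047, beta = 0.188.
- **Definition under the table:** "R – combined drug rejection number after both stages".

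The synopsis and section 4.1 repeat the stage 1 rule and the total of 31 but give no final cut-off. Section 6.2, on the primary endpoint, gives none either. Section 9.3 is therefore the only place where the final rule appears.

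**The concern.** The text and the table use the same convention at stage 1: R1 = 3 in the table and > 3 in the text. Applied to the final stage, R = 10 should become > 10, but the text says > 11. The written rule therefore asks for one more success than the computed design, and the alpha and beta printed in the Optimum row do not describe it.

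Two things are at stake. First, the power the plan reports is not the power of the rule it states. Second, if the trial finishes with exactly 11 of 31 patients progression-free at 4 months, the same section supports both a negative and a positive conclusion, and someone would have to choose between them after seeing the result. The rationale for Amendment 1 in the protocol history says that 4-month PFS is the only endpoint the study assesses with a pre-identified error risk. Two different cut-offs leave that risk undefined.

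**Working it through.** **Inputs**, all from section 9.3: p0 = 0.22, p1 = 0.45, n1 = 12, r1 = 3, n = 31 (so 19 patients in stage 2). The final rejection number r is 10 from the table or 11 from the text.

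**Formula.** The drug succeeds if X1 > r1 and X1 + X2 > r, so

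P(success | p) = Σ over x1 = 4…12 of Bin(x1; 12, p) × P(X2 > r − x1), with X2 ~ Bin(19, p).

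Setting p = 0.22 gives alpha and p = 0.45 gives power.

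**Step 1. Early termination and average N.** At p = 0.22 the probabilities of 0, 1, 2 and 3 successes in 12 are 0.0507, 0.1717, 0.2663 and 0.2503. They sum to PET = 0.739. Average N = 12 + (1 − 0.739) × 19 = 16.96. Both match the table.

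**Step 2. The meaning of R.** The other two rows of the table test the reading that the drug is rejected at R or fewer.

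| Row | Success at | alpha | beta | Table |
|---|---|---|---|---|
| Single stage, 26/9 | > 9 | 0.043 | 0.194 | 0.043, 0.194 |
| Single stage, 26/9 | ≥ 9 | 0.098 | 0.102 | no match |
| Minimax, 7/0 and 26/9 | > 9 | 0.042 | 0.199 | 0.042, 0.199 |

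R is therefore the largest count at which the drug is still rejected, and success requires more than R.

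**Step 3. Power at p = 0.45, term by term.** Each contribution is Bin(x1; 12, 0.45) × P(X2 > r − x1).

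| x1 | Bin(x1; 12, 0.45) | P(X2 > 10 − x1) | Contribution, r = 10 | P(X2 > 11 − x1) | Contribution, r = 11 |
|---|---|---|---|---|---|
| 4 | 0.1700 | 0.8273 | 0.1406 | 0.6831 | 0.1161 |
| 5 | 0.2225 | 0.9223 | 0.2052 | 0.8273 | 0.1841 |
| 6 | 0.2124 | 0.9720 | 0.2064 | 0.9223 | 0.1959 |
| 7 | 0.1489 | 0.9923 | 0.1478 | 0.9720 | 0.1448 |
| 8 | 0.0762 | 0.9985 | 0.0761 | 0.9923 | 0.0756 |
| 9–12 | 0.0356 | about 1 | 0.0356 | about 1 | 0.0355 |
| **Sum** | | | **0.8117** | | **0.7519** |

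**Step 4. Both rules at both rates.**

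| Final rule | alpha (p = 0.22) | Power (p = 0.45) | beta |
|---|---|---|---|
| > 10 of 31 (table, R = 10) | 0.0468 | 0.8117 | 0.1883 |
| > 11 of 31 (text) | 0.0221 | 0.7519 | 0.2481 |

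The first line reproduces the printed 0.047 and 0.188. The second line does not.

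**Step 5. Where the rules disagree.** They differ only if the trial continues past stage 1 and ends on exactly 11 successes. That probability is the difference between the two lines: 0.8117 − 0.7519 = 0.060 at p = 0.45 (allowing for rounding), and 0.0468 − 0.0221 = 0.025 at p = 0.22.

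**Step 6. Optimality.** A search over n1, r1, n and r with alpha at most 0.05 and beta at most 0.20 returns 3/12 and 10/31 as the design with the smallest expected sample size under p0 (16.96). The table is therefore correct for the stated inputs, and the discrepancy lies in the text.

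**The case against.** The strongest counter-argument is that the written rule errs on the safe side. Its alpha of 0.022 is well inside the 0.05 limit, so it cannot produce more false claims of activity than planned. The power loss is modest: with > 11 of 31, power is 0.783 at P = 0.46 and 0.811 at P = 0.47. The two rules differ at a single outcome, and the sample size, stage 1 rule, PET and average N are untouched. All of this is true and limits the size of the problem. It does not make the stated error rates those of the stated rule.

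The conflict may be only a slip, with at least 11 turned into > 11, or a sign damaged in the PDF conversion. A slip is plausible. Conversion damage is less so, because the same paragraph keeps its ≤ and ≥ signs intact. In either case the text as it stands defines the wrong cut-off.

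One coincidence should be set aside. If the stage 1 stop is ignored, > 11 of 31 has power 81.1%, close to 1 − 0.188. Its alpha is then 0.026, not 0.047, and the planned futility stop has been left out, so this does not rescue the text.

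A fair point about the remedy also stands. This is an open-label, single-arm trial first approved in 2013, and the current version is dated April 2019. The documents do not give enrolment status. Lowering the threshold from 12 to 11 after results are visible could look like relaxing the criterion, so the reason and timing of the correction matter.

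**Conclusion.** The concern holds. The adopted design in section 9.3 is 3/12 and 10/31, with success at 11 or more. The text requires 12 or more. The written rule has alpha 0.022 and power 75.2%. The tabulated design has alpha 0.047 and power 81.2% (1 − 0.188), and the plan's target is 80%. The loss is 6.0 percentage points of power, and the false-negative risk at P = 0.45 rises from 18.8% to 24.8%.

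These figures assume that the stage 1 stop is applied as planned and that exactly 31 patients are analysed. Section 6.2 restricts evaluability to patients who complete at least 2 cycles. If that makes the analysed number differ from 31, neither power figure applies exactly, but the contradiction between text and table remains.

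**What to change.** Make the final rule and the operating characteristics in section 9.3 describe the same design, in one of two ways:

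- **Match the table:** change the text to success at > 10 of 31, with 11 or more added in parentheses. The tabulated alpha of 0.047 and beta of 0.188 then apply.
- **Keep the text:** retain > 11 of 31, with 12 or more added in parentheses. State alpha 0.022 and power 75% (beta 0.248), and note that the design no longer meets the beta = 0.20 target.

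The first restores the computed design. The second avoids lowering the threshold if outcome data have already been seen. If the first is chosen, the amendment should record that it corrects the text to the original sample-size calculation, say how much outcome data was available at the time, and be made without reference to those data.

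The cost is one number, or one sentence of operating characteristics, plus the amendment record. The sample size, the stage 1 rule and patient procedures do not change. It should be settled before the final count is known.

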9.4 PLANNED ANALYSES

Survival data will be analyzed using parametric (exponential) and non-parametric (Kaplan-Meier) methods. Exact methods for providing confidence intervals for proportions “surviving” landmarks will be used as needed. Statistical software will be SAS (and others as merited) and analysis will be conducted under the supervision of [name], in the Biostatistical Core Facility at Northwestern University.

Descriptive statistics (mean, standard deviation, mean change from baseline, etc.) will be presented for laboratory values. Detailed examination of AEs by NCI CTCAE grade and frequency tabulation will be presented. Missing data for partial dates on AEs or concomitant medications may be imputed.

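### Section 9.3 lets a positive result conclude that P > 0.45, but the test controls error only at P = 0.22; 0.45 is the rate used for power

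*Combined protocol and SAP*

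**What the plan says.** Section 9.3 sets up an optimal Simon two-stage design for P, the probability of 4-month progression-free survival. The null is P ≤ 0.22 and the alternative is P ≥ 0.45, with target alpha 0.05 and beta 0.20. Twelve patients enter stage 1, and more than 3 successes take the trial to 31. The final rule begins "If > 11 out of 31 patients achieve progression-free survival of 4 months". On that event the trial rejects P ≤ 0.22 "and conclude that $P > 0.45".

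The definitions under the design table give the two rates their roles. Alpha is the "probability of rejecting that $P < P0$ when this is true". P0 is the "response proportion P of a poor drug" and P1 the "response proportion P of a good drug"; beta is tied to P1. No section gives a test or an error rate against 0.45.

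Section 9.4 says that exact confidence intervals for proportions at "landmarks will be used as needed". It makes no firm commitment for the primary endpoint.

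**The concern.** Rejecting a null hypothesis at 0.22 supports P > 0.22. It does not place P above the rate chosen for the power calculation. The stated hypotheses leave the range from 0.22 to 0.45 in neither one, and the conclusion treats that range as excluded whenever the null is rejected.

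This is the only decision rule for the primary endpoint, so it is the sentence a report would follow. A barely positive trial could be reported with an overstated 4-month rate. The figure 0.45 also has a meaning inside the protocol: Section 1.1 gives 45% as the 4-month PFS in the phase II trial of weekly paclitaxel. The documents do not say that P1 was taken from there, but a reader could take a conclusion of P > 0.45 as a claim to have exceeded that result.

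**Working it through.** **Inputs (all from Section 9.3).** n1 = 12, continue if more than 3 successes; N = 31, so 19 patients in stage 2; P0 = 0.22; P1 = 0.45. The text requires more than 11 of 31 (k = 12 or more). The table's optimum row has R = 10 (k = 11 or more). That mismatch is a separate point; both cut-offs are shown so that the result does not depend on it.

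**Formula.** P(success | p) = Σ over x = 4 to 12 of C(12,x) p^x (1−p)^(12−x) × P(Bin(19,p) ≥ k − x).

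**Step 1: reproduce the plan's figures.** With k = 11:
- early stopping at p = 0.22: P(Bin(12, 0.22) ≤ 3) = 0.739;
- average N = 12 + 19 × (1 − 0.739) = 16.96;
- alpha = P(success | 0.22) = 0.0468;
- power = P(success | 0.45) = 0.8117, so beta = 0.188.

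All four agree with the optimum row. They confirm that alpha is evaluated at 0.22 and that 0.45 is used only for beta.

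**Step 2: how often the trial would conclude P > 0.45 when that is false.** The last two columns give the share of those positive results in which the observed rate is itself below 0.45. These are totals of 12–13 under the text rule and 11–13 under the table rule; 14/31 is 45.2%.

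| True P | Text rule (>11) | Table rule (>10) | Share below 0.45, text | Share below 0.45, table |
|---|---|---|---|---|
| 0.30 | 0.166 | 0.252 | 0.1157/0.1660 = 70% | 0.2016/0.2519 = 80% |
| 0.35 | 0.350 | 0.456 | 0.1987/0.3495 = 57% | 0.3050/0.4559 = 67% |
| 0.40 | 0.564 | 0.657 | 0.2392/0.5641 = 42% | 0.3324/0.6573 = 51% |

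At true P = 0.449 the probabilities are 0.749 (text) and 0.809 (table). Read as a test of 0.45, the rule therefore has an error rate of about 75% to 81% just below that value.

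**Step 3: what the smallest positive results show.** The first interval is Clopper-Pearson, treating the 31 patients as one sample. The second allows for the two stages by ranking every stage 1 stop below every stage 2 total. Its lower limit solves P(total ≥ k | p) = 0.025 and its upper limit solves 1 − P(total ≥ k + 1 | p) = 0.025.

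| Result | Observed | Exact 95% CI, single sample | Exact 95% CI, two-stage |
|---|---|---|---|
| 11/31 (table rule only) | 35.5% | 19.2–54.6% | 20.0–58.6% |
| 12/31 | 38.7% | 21.8–57.8% | 22.4–60.1% |
| 13/31 | 41.9% | 24.5–60.9% | 24.9–62.1% |

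Every interval contains 0.45 and extends well below it. These results do not rule out 0.45 and do not establish that P exceeds it.

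**Step 4: the count that would support P > 0.45.** At p = 0.45 the two-stage tail is P(total ≥ 19) = 0.0505 and P(total ≥ 20) = 0.0227. So 20/31 (64.5%) is the smallest count that meets one-sided 5%, and it also meets one-sided 2.5%. The text rule asks for 12.

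**The case against.** The strongest reply is that the sentence is shorthand. Section 9.3 poses a two-point problem with nothing between 0.22 and 0.45, and its definition of beta uses P > P1 as the label for the good-drug hypothesis. On that reading the sentence means only that the design alternative is accepted. This is plausible, but the plan does not say so, and what it states is a strict numerical inequality.

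Second, the percentages in Step 2 are the ordinary power curve of the design between 0.22 and 0.45. That is correct. A Simon design is expected to pass many drugs in that range, and the test is working as intended. The percentages measure the unsupported clause and nothing else.

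Third, the quoted conclusion is attached only to the >11 rule, so 11/31 and the table-rule column apply only if R = 10 is what is used. That also stands; the point holds on 12/31 and 13/31 alone.

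Fourth, other parts of the plan limit the harm. Section 2.1 frames the objective as estimation, Section 9.4 allows Kaplan-Meier estimates and exact intervals, and Section 10.10 requires the biostatistician's approval before a manuscript is submitted. These make misreporting less likely, but none of them corrects the sentence, and an interval reaching below 0.45 would contradict it.

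**Conclusion.** The point holds. The supported conclusion from a positive trial is P > 0.22, with one-sided type I error 0.022 under the text rule or 0.047 under the table rule. The further claim of P > 0.45 has no error control: it would be made wrongly 16.6% to 56.4% of the time for true rates from 0.30 to 0.40 under the text rule, and 25.2% to 65.7% under the table rule. It would be made on observed rates as low as 38.7% (text) or 35.5% (table).

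The calculations assume independent binomial outcomes, exactly 12 and 31 patients, and the stage 1 rule as written. The error lies in the stated conclusion and leaves the design's operating characteristics intact. It should be corrected because it concerns what the primary analysis is said to show.

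**What to change.** - **Section 9.3:** change the end of the decision rule so that success rejects P ≤ 0.22 and concludes that P > 0.22. Add that 0.45 is the rate at which power was computed. If the sentence was meant as shorthand for accepting the design alternative, say that explicitly and remove the inequality.
- **Section 9.4:** replace the optional wording with a commitment for the primary endpoint. Report the observed 4-month PFS proportion with an exact confidence interval, state its level, and describe the size of effect from that interval. An interval that accounts for the two stages is preferable, although it moves the lower limit for 12/31 only from 21.8% to 22.4%.

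The cost is one sentence in 9.3 and a few words in 9.4. Sample size, stopping rule, alpha and power stay as they are; the pre-specified conclusion becomes less favourable.
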